## 7.6. Medical History

Medical history verbatim terms captured via the EDC system will be mapped to System Organ Class (SOC) and Preferred Term (PT) using MedDRA version 25.0. Any new, untoward, or worsening medical or psychiatric condition reported after first administration of the investigational product is to be captured as an adverse event.

Medical history events will be summarized by SOC and PT using the safety population. The summary will present the number and percent of subjects having each event. Subjects may have more than one event per SOC and PT. However, a subject is counted once if one or more events at the same level of SOC and PT is reported for the subject. The summary will be displayed in descending order of incidence of SOC and then descending order of PT within SOC.

A listing of medical history events will also be provided.

## 7.7. Prior and Concomitant Medications

Prior and concomitant medication verbatim terms captured via the EDC system will be mapped to Anatomical Therapeutic Chemical (ATC) classification and preferred name using the World Health Organization Drug (WHODrug) Dictionary Global March 2022 release.

Prior and concomitant medications (defined below) will be summarized separately by WHO ATC classification (using ATC4 and then using the closest available parental ATC classification if ATC4 is not available) and preferred name using the safety population.

- **Prior Medication:** Medications with a start date prior to first dose date will be considered as prior medications regardless of when the medications ended or whether the medications are ongoing.
- **Concomitant Medication:** Prior medications that continue to be taken on or after the first dose date or new medications with a start date on or after first dose date will be considered concomitant medications.

Note that these definitions are not mutually exclusive in that it is possible for a medication to be both prior and concomitant if that medication started prior to first dose and continued after first dose, such as with for example a high blood pressure medication.

These summaries will present the number and percent of subjects using each medication. Subjects may have more than one medication per ATC classification and preferred name. However, a subject is counted once if one or more medications at the same level of ATC classification and preferred name is reported for the subject. Each summary will be displayed in descending order of incidence of ATC classification and then descending order of preferred name within ATC classifications.

A listing of prior and concomitant medications will also be provided. In the listing, each medication will be marked as prior, concomitant, or prior and concomitant.

## **7.8. Duration and Compliance**

Treatment Duration, Study Duration, Treatment Compliance, and Morning Meal Compliance will be derived as stated in Section 5.2 of this SAP. A summary will be provided for Treatment Duration, Study Duration, and Compliance as continuous, and for Morning Meal Compliance as categorical, using the safety population.

A listing of Treatment Duration, Study Duration, Treatment Compliance, and Morning Meal Compliance, and a listing of dosing diary information, will also be provided. Additionally, a listing of study drug administration (in clinic) and a listing of drug accountability will be provided.

## **8. Efficacy Analysis**

The efficacy objectives of this study are to evaluate the efficacy of ANC-501 capsules in subjects with MDD. There will be no imputations for missing data except as outlined in Section 5.1 of this SAP.

The efficacy endpoints will be summarized using descriptive statistics. All efficacy analyses will be based on the efficacy population.

Results for efficacy parameters will also be listed by subject according to the relevant section in this SAP.

### **8.1. Efficacy Parameters**

The primary efficacy parameter is the change from baseline to Day 56 in the Montgomery-Åsberg Depression Rating Scale (MADRS) total score.

Secondary parameters for efficacy to be considered include:

- Change from baseline in MADRS total score at all scheduled post-baseline visits

- Percentage of MADRS responders ( $\geq 50\%$  reduction in total score) at all scheduled post-baseline visits
- Percentage of MADRS remitters (total score  $\leq 10$ ) at all scheduled post-baseline visits
- Change from baseline in Hamilton Anxiety Scale (HAM-A) total score at all scheduled post-baseline visits
- Change from baseline in Clinical Global Impression-Severity (CGI-S) score at all scheduled post-baseline visits
- Short Form-Health Survey (36-item) (SF-36) total score and subscale scores from Baseline to Day 56 and at all time points
- Percentage of Clinical Global Impression-Improvement (CGI-I) improvers (“Very much improved” or “Much improved”) at all scheduled post-baseline visits
- Patient Global Impression of Improvement (PGI-I) score at Day 56

Exploratory parameters for efficacy to be considered include:

- Change in Hamilton Depression Rating Scale (6-item) (HAMD-6) scores from baseline across all time points
- Change in General Anxiety Disorder (7-item) (GAD-7) from baseline across all time points

## 8.2. Primary Efficacy Analysis

The primary efficacy objective of this study is to evaluate the effect of treatment with ANC-501 capsules on depressive symptoms in subjects with MDD.

### 8.2.1. MADRS Total Score – Day 56 Only

The primary efficacy endpoint is the change from baseline to Day 56 in Montgomery-Åsberg Depression Rating Scale (MADRS) total score.

The MADRS contains 10 questions, each rated on a 7-point scale. The total score is calculated by summing the 10 item scores and will range from 0 to 60. A higher score indicates more severe depression.

Summary statistics on the observed and change from baseline MADRS total score will be displayed at baseline and Day 56. In addition, a one-sample two-sided t-test will be performed and the 95% confidence interval and p-value for the mean change from baseline (i.e., mean difference) will be included.

MADRS total score will be shown on the listing described in Section 8.3.1 of this SAP.

One figure will be provided showing a line plot of baseline MADRS total score and Day 56 MADRS total score for all subjects, one line per subject.

### **8.3. Secondary Efficacy Analysis**

The secondary efficacy objective of this study is to evaluate the effect of ANC-501 at scheduled visits and percent reduction in total symptom scores compared with baseline.

#### **8.3.1. MADRS Total Score – Scheduled Visits**

MADRS scores will be collected at Screening, Day 1, Day 8, Day 15, Day 29, Day 43, Day 56, and Day 70. The total score will be calculated as described in Section 8.2.1.

Summary statistics on the observed and change from baseline MADRS total score will be displayed at baseline and all scheduled visits. Additionally, summary statistics on the observed and change from baseline MADRS item scores will be displayed at baseline and all scheduled visits.

A listing of MADRS total score, MADRS responder (Yes, No) as described in Section 8.3.2 of this SAP, MADRS remitter (Yes, No) as described in Section 8.3.3 of this SAP, and the ten MADRS item scores will also be provided. MADRS responder and MADRS remitter will appear in the listing starting on Day 8.

Two figures will be provided, one showing the mean MADRS total score at baseline and at each post-baseline scheduled visit, and the other showing the mean change from baseline MADRS total score at baseline (i.e., zero) and each post-baseline scheduled visit. Both figures will include standard error bars at baseline and each post-baseline visit, where standard error = standard deviation /  $\sqrt{n}$ , except for mean change from baseline in MADRS total score at baseline.

#### **8.3.2. MADRS Responders**

MADRS responders are defined as subjects who experienced a  $\geq 50\%$  reduction in total score from baseline. The total score will be calculated as described in Section 8.2.1.

For all subjects with a MADRS measurement at the corresponding visit, the frequency and percentage of MADRS responders (Yes, No) will be displayed at all scheduled post-baseline visits. MADRS responders will be shown on the listing described in Section 8.3.1 of this SAP.

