9.3. Analysis Populations

For the purposes of analysis, the following populations are defined:

Table 5: Definitions of Analysis Populations

Analysis Population	Definition
Safety	Includes all subjects who received at least one dose of ANC-501. This is the primary population for exposure and safety analyses.
Efficacy	Includes all subjects who received at least one dose of ANC-501 and have at least one post-baseline efficacy evaluation. This is the primary population for efficacy endpoints.

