## 4. Analysis Populations

**Safety Population (SAF):** The Safety population will consist of all subjects who received at least one dose of ANC-501. This population will be used for all Safety analyses.

Enrolled Subjects: The date the first dose of ANC-501 is administered is the date a subject is considered enrolled into the study. Enrolled subjects and the safety population are equivalent.

**Efficacy Population (EFF):** The Efficacy population will consist of all subjects who received at least one dose of ANC-501 and have completed treatment. This population will be used for all Efficacy analyses.

EFF differs from the protocol due to two subjects who were discontinued near the beginning of the study due to a failed Day 1 drug screen.

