## **5.1. Handling Missing Data**

For incomplete dates related to adverse events and concomitant medications, the dates will be imputed as follows:

- Incomplete start dates missing day with known month will be imputed as the later of (a) day of first dose started in that month or (b) first of the month.
- Incomplete start dates missing month and day will be imputed as the later of (a) month and day of first dose started in that year or (b) January 1.
- Dates missing year regardless of month or day will be considered as missing.
- An unknown start time with known or imputed date will be imputed with a time of 23:59 for events or medications on Day 1 or as 00:00 on other days.
- An unknown end time with known or imputed date will be imputed the same as a missing start time unless the event or medication is ongoing.
- Events with completely unknown start dates will be considered as treatment-emergent adverse events unless otherwise indicated by a known end date.
- Medications with completely unknown start dates will be considered as concomitant medications unless otherwise indicated by a known end date.
- Any imputed start date or time must come before any known end date or time.
- Missing dates, date parts, and time will be shown as missing in the listings.

For missing values not described in this section of the SAP, imputation will not be performed.

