### **8.3.3. MADRS Remitters**

MADRS remitters are defined as subjects with a total score  $\leq 10$ . The total score will be calculated as described in Section 8.2.1.

For all subjects with a MADRS measurement at the corresponding visit, the frequency and percentages of MADRS remitters (Yes, No) will be displayed at all scheduled post-baseline visits. MADRS remitters will be shown on the listing described in Section 8.3.1 of this SAP.

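### MADRS response and remission rates are observed-case rates among treatment completers, with no display that counts missing scores as non-response, so they may overstate response

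*SAP*

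**What the plan says.** For response, SAP 8.3.2 reads: "For all subjects with a MADRS measurement at the corresponding visit, the frequency and percentage of MADRS responders (Yes, No) will be displayed". SAP 8.3.3 uses the same rule for remission: "For all subjects with a MADRS measurement at the corresponding visit, the frequency and percentages of MADRS remitters". Both are shown at every scheduled visit after baseline. For MADRS that runs to Day 70, two weeks after dosing ends.

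Scores are not imputed. SAP 5.1 covers partial dates and times and then closes the list: "For missing values not described in this section of the SAP, imputation will not be performed". SAP 8 repeats this for efficacy: "There will be no imputations for missing data except as outlined in Section 5.1 of this SAP". Neither section describes a sensitivity display.

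The population is restricted as well. SAP 4 states: "The Efficacy population will consist of all subjects who received at least one dose of ANC-501 and have completed treatment". Protocol 9.3 (Table 5) is wider: "Includes all subjects who received at least one dose of ANC-501 and have at least one post-baseline efficacy evaluation". The SAP attributes the difference to two positive drug tests: "EFF differs from the protocol due to two subjects who were discontinued near the beginning of the study due to a failed Day 1 drug". The SAP wording, however, removes every non-completer, not only those two.

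Footnote a of the schedule of events, in both documents, asks subjects who stop early to attend for the Day 56 procedures, which include a MADRS. Protocol 9.4.1 left missing-data methods to the SAP.

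**The concern.** Two filters act in sequence. The completer rule takes out anyone who stopped treatment, even where an early-termination score exists. The per-visit denominator then takes out any remaining subject without a score at that visit. In neither case is the subject counted as a non-responder.

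Some of the reasons for stopping in Protocol 7.1, such as unacceptable toxicity or a need for other antidepressant therapy, make it plausible that those who leave respond less often than those who stay. Response and remission are named secondary endpoints. With a single arm, no control group is subject to the same filters, so any overstatement passes straight into the reported rate. Denominators can also differ between visits, so a trend over time may partly reflect who was measured.

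**Working it through.** **Inputs.** From the documents: up to 20 enrolled (SAP 6.1), two early discontinuations (SAP 4), observed-case denominators (SAP 8.3.2, 8.3.3) and no score imputation (SAP 5.1, 8). The plan states no response rate, remission rate or missingness rate, so there is no figure of its own to reproduce. Assumed here: a population of N = 18 (20 − 2), m subjects missing a score at the visit, and r responders among those observed.

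**Step 1: observed-case rate against missing counted as non-response, same population.** The rates are r/(N − m) and r/N. The gap is r/(N − m) − r/N = [r/(N − m)] × (m/N), the observed rate times the fraction missing. It cannot be negative and is zero when m = 0.

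| m | Observed-case | Missing as non-response | Gap (points) |
|---|---|---|---|
| 1 | 5/17 = 29.4% | 5/18 = 27.8% | 1.6 |
| 1 | 8/17 = 47.1% | 8/18 = 44.4% | 2.6 |
| 2 | 5/16 = 31.25% | 5/18 = 27.8% | 3.5 |
| 2 | 8/16 = 50.0% | 8/18 = 44.4% | 5.6 |
| 4 | 4/14 = 28.6% | 4/18 = 22.2% | 6.3 |
| 4 | 7/14 = 50.0% | 7/18 = 38.9% | 11.1 |

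Gaps are taken before rounding.

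**Step 2: observed-case rate against the true rate.** Let p be the true rate, and q1 and q0 the chances that a responder and a non-responder are missing. The expected observed-case rate is p(1 − q1) / [p(1 − q1) + (1 − p)(1 − q0)]. With p = 40%:

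- q1 = q0 = 10%: 0.36/(0.36 + 0.54) = 40.0%, no bias.
- q1 = 5%, q0 = 20%: 0.38/(0.38 + 0.48) = 44.2%, upward.
- q1 = 20%, q0 = 5%: 0.32/(0.32 + 0.57) = 36.0%, downward.

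The sign depends on who is missing. The data alone give only bounds: with N = 18, m = 2 and r = 8, the rate lies between 8/18 = 44.4% and (8 + 2)/18 = 55.6%, around a displayed 50.0%.

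**Step 3: the two filters separately.** Assume 20 dosed and 9 responders, all among completers. All dosed: 9/20 = 45.0%. With two non-completers removed by the population rule: 9/18 = 50.0%, a rise of 5.0 points. With one completer also missing the visit: 9/17 = 52.9%, a further 2.9. With four or six non-completers and no missed visits: 9/16 = 56.25% or 9/14 = 64.3%.

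**Step 4: would restoring the protocol population be enough?** Suppose the two non-completers qualify for the protocol population but have no later MADRS. Under the per-visit rule they leave the later denominators again, and the rate stays at 9/18 = 50.0%. Only a fixed denominator gives 9/20 = 45.0%. The population and the denominator have to change together.

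**The case against.** The best counter-argument is about cause. A reader might infer that the per-visit denominator is what drops subjects who stop for lack of effect or intolerance. Under the current SAP it is not: the completer definition has already removed them. Within that population the visit rule touches only completers who miss a visit or are lost by Day 70. That stands, and it makes the completer rule probably the larger source of selection.

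A reader might also infer that the rates are certainly biased upward. The documents give neither a rate nor a mechanism of missingness, and Step 2 shows that no bias or a downward bias is possible. Counting a completer's sporadic missed visit as non-response can itself understate response. Step 3 assumes that nobody removed was a responder, and the two known cases left over a drug screen, not lack of effect. Its largest figures should not be read as estimates.

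The early-termination visit would supply a score for some stoppers. That is correct, but attendance is not assured, intermediate visits would still be missing, and the present population definition excludes those scores from the summaries.

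Finally, these are descriptive secondary endpoints. Counts accompany the percentages, responder status is listed by subject from Day 8, and discontinuations are tabulated. This limits the harm, since much can be recomputed. It does not put the alternative rate in the table, and the SAP does not say whether the MADRS listing covers subjects outside the efficacy population.

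**Conclusion.** The point holds in a conditional form. The planned rates describe completers with a score at the visit, and nothing in the plan shows how they change when missing scores count as non-response. On the same population the planned rate is equal to or higher than that alternative, by construction. Whether it exceeds the true rate depends on non-responders being missing more often, which is plausible but not documented.

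The visit rule alone is worth about 2 to 3 points with 1 missing of an assumed 18, 4 to 6 with 2, and 6 to 11 with 4, at observed rates of about 30% to 50%. With none missing it is worth nothing. The completer rule comes on top: each subject is 1/20 = 5 points of a full sample of 20. No type I error or between-arm comparison is affected. This is a reporting weakness worth correcting, not a flaw that undermines the study.

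**What to change.** In SAP 8.3.2 and 8.3.3:

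- Report both rates on a fixed denominator: the protocol-defined efficacy population (dosed, with one or more efficacy assessments after baseline).
- Use the early-termination MADRS for Day 56 where it exists, and footnote how many values come from that visit.
- Count a missing MADRS as non-responder and non-remitter.
- Keep the observed-case percentage beside it, and show the numbers observed and missing at each visit.

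This needs a few sentences and some extra table rows, with no new data. The price is a slightly less favourable rate, which may be too conservative where a responder misses an isolated visit; the observed-case column makes that visible. If the database is already locked, SAP 5 would require the added display to be labelled post hoc.

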### **8.3.3. MADRS Remitters**

MADRS remitters are defined as subjects with a total score  $\leq 10$ . The total score will be calculated as described in Section 8.2.1.

For all subjects with a MADRS measurement at the corresponding visit, the frequency and percentages of MADRS remitters (Yes, No) will be displayed at all scheduled post-baseline visits. MADRS remitters will be shown on the listing described in Section 8.3.1 of this SAP.

### **8.3.4. Hamilton Anxiety Scale (HAM-A)**

Hamilton Anxiety Scale (HAM-A) scores will be collected at Screening, Day 1, Day 8, Day 15, Day 29, Day 43, Day 56, and Day 70. HAM-A consists of 14 questions, each rated on a 5-point scale. The total score is calculated by summing the responses to all 14 questions and will range from 0 to 56. A higher score indicates more severe anxiety.

Summary statistics on the observed and change from baseline in HAM-A total score will be displayed at baseline and all scheduled visits.

A listing of the fourteen HAM-A items as well as the HAM-A total score will also be provided.

One figure will be provided showing the mean HAM-A total score at baseline and at each post-baseline scheduled visit. The figure will include standard error bars at baseline and each post-baseline visit, where standard error = standard deviation /  $\sqrt{n}$ .

### **8.3.5. Clinical Global Impression-Severity (CGI-S)**

The Clinical Global Impression-Severity (CGI-S) score will be collected at Screening, Day 1, Day 8, Day 15, Day 29, Day 43, Day 56, and Day 70. CGI-S consists of one question, where the clinician is asked, “Considering your total clinical experience with this particular population, how mentally ill is the patient at this time?” This question is rated on a scale from 0 to 7, where a higher score indicates greater severity of mental illness, as follows:

- 0 = Not assessed
- 1 = Normal, not at all ill
- 2 = Borderline mentally ill
- 3 = Mildly ill
- 4 = Moderately ill
- 5 = Markedly ill

6 = Severely ill

7 = Among the most extremely ill patients

Summary statistics on the observed and change from baseline in the CGI-S score will be displayed at baseline and all scheduled visits. A value of zero will be treated as missing and not included in the summary statistics.

CGI-S score will be shown on the listing described in Section 8.3.7 of this SAP.

One figure will be provided showing the mean CGI-S score at baseline and at each post-baseline scheduled visit. The figure will include standard error bars at baseline and each post-baseline visit, where standard error = standard deviation /  $\sqrt{n}$ .

#### **8.3.6. Short Form-Health Survey (36-item) (SF-36)**

Short Form-Health Survey (36-item) (SF-36) consists of 36 questions. Each item's score will be recoded to a value on a scale from 0 to 100. For items 1, 2, 20, 22, 34, and 36, the scores are recoded as 1=100, 2=75, 3=50, 4=25, 5=0. For items 3, 4, 5, 6, 7, 8, 9, 10, 11, and 12, scores are recoded as 1=0, 2=50, 3=100. For items 13, 14, 15, 16, 17, 18, and 19, scores are recoded as 1=0 and 2=100. For items 21, 23, 26, 27, and 30, scores are recoded as 1=100, 2=80, 3=60, 4=40, 5=20, 6=0. For items 24, 25, 28, 29, and 31, scores are recoded as 1=0, 2=20, 3=40, 4=60, 5=80, 6=100. For items 32, 33, and 35, scores are recoded as 1=0, 2=25, 3=50, 4=75, 5=100.

For each of the 8 scales, the corresponding items are averaged for a scale score. Items that are left blank (missing data) are not considered when calculating the scale scores.

The scales and corresponding items are as follows: physical functioning (PF) (items 3-12), role limitations due to physical health (RP) (items 13-16), role limitations due to emotional problems (RE) (items 17-19), energy/fatigue (ENGY) (items 23, 27, 29, 31), emotional well-being (EMWB) (items 24-26, 28, 30), social functioning (SF) (items 20, 32), Pain (PAIN) (items 21-22), and general health (GH) (items 1, 33-36).

The physical health summary measure includes four scales: PF (10 items), RP (4 items), PAIN (2 items), and GH (5 items). The mental health summary measure includes four scales: RE (3 items), ENGY (4 items), EMWB (5 items), and SF (2 items). The total score is an average of all 36 items. A higher score indicates a more favorable physical and mental health state.

All SF-36 summaries, listings, figures, and analyses will be described in a separate analysis plan and performed separately by an external vendor, including any analysis of orienting questions.

